In the dose-finding Phase 1 portion of the study, dose levels of cabozantinib will be tested in cohorts of 3 subjects each using the 3+3 dose-finding design, with the starting dose of 40mg once daily, with potential dose escalation to 60 mg, or de-escalating to 20 mg daily. The daily dose of cabozantinib will not be increased to more than 60 mg per day. The DLT period will include all subjects enrolled to the phase 1 component of the study. The DLT period is defined as beginning on C1D8 and continuing until 28 days after completion of concurrent radiation therapy and cabozantinib. If no dose-limiting toxicity (DLT) is observed at the starting dose in the first 3 subjects, the next dose cohort would enroll subjects at 60 mg. If 1 DLT is observed any dose cohorts in the first 3 subjects, then additional 3 subjects will be enrolled at that dose level. If ≤ 1 of 6 subjects experience a DLT at the starting dose or higher, enrollment would continue to the next higher dose level. The first 3 subjects of each cohort must complete their DLT period prior to expanding the cohort to include additional subjects to ensure a second DLT is not seen in the first 3 subjects. If ≤ 1 of 6 subjects experience a DLT at the starting dose or higher, enrollment would continue to the next higher dose level.

If ≥ 2 subjects experience a DLT at dose level higher than the starting dose, enrollment will be discontinued for that dose cohort and the previous dose level would be declared the maximum

tolerated dose (MTD). If ≥ 2 subjects experience a DLT at the starting dose of 40 mg once daily (and any lower dose level), further enrollment at that dose level will be discontinued and cabozantinib will be reduced to the next planned dose level.

If a subject is considered Not Evaluable due to withdrawal for reasons other than toxicity during the DLT Period, they will be replaced.

The MTD of cabozantinib is the highest dose level at which ≤ 1 of 6 (or 0 out of 3) subjects experienced a DLT, thus a target DLT rate of roughly 17%. It is possible that the MTD is not reached in this study (e.g., if no DLT observed in the first 3 subjects at 60 mg daily). Recommended Phase 2 dose (RP2D) is identified based of the totality of safety and efficacy data. Once the dose-finding portion of the study is concluded and RP2D is identified, subjects receiving a lower dose may be allowed to receive cabozantinib at the RP2D, based on the investigator judgment.

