7.1.2. Cabozantinib Dose Modification and Stopping Rules

The following should be taken into consideration in decisions regarding dose modifications (reductions or interruption):

- As a general approach all AEs should be managed with supportive care at the earliest signs of toxicity considered related to the study treatment. Should this be ineffective, dose interruptions and/or reductions should be considered to prevent worsening of toxicity.
- The assigned starting dose for cabozantinib is 40 mg/day. The dose level may go to -1 as seen in Table 4. Further dose reductions beyond 20 mg daily are not permitted.
- Dose modification criteria for cabozantinib are shown in Table 5 and 6. Dose interruptions and/or reductions should be implemented for unacceptable toxicity. Doses may be modified at any time while a subject is on treatment.

- Dose reductions or interruptions may also occur in the setting of lower grade toxicity if the investigator feels it is in the interest of a subject's safety and will optimize drug tolerability.
- Interruption of cabozantinib treatment for cabozantinib-related AEs may occur at any time per investigator discretion. If treatment is interrupted due to related AEs for more than 6 weeks, cabozantinib should be discontinued.

Dose interruptions for reason(s) other than treatment-related AEs (e.g., surgical procedures, upper respiratory infection, common cold) can be longer than 6 weeks per the discretion of the investigator.

Guidelines for the management of specific AEs are provided in Section 10.2.2.

Table 5 - Dose Modifications of Cabozantinib

Assigned Dose	First Dose Level Reduction	Second Dose Level Reduction
60-mg cabozantinib oral qd*	40-mg cabozantinib oral qd	20-mg cabozantinib oral qd
40-mg cabozantinib oral qd	20-mg cabozantinib oral qd	No further dose reductions
20-mg cabozantinib oral qd**	No further dose reductions	No further dose reductions

*qd, once daily

**Cabozantinib will be discontinued if a qd dose of 20-mg cabozantinib daily (minimum dose) is not tolerated

Table 6 - Dose Modifications of Cabozantinib for Treatment-Related AEs

CTCAE v.5.0 Grade	Recommended Guidelines for Management ^a
Grade 1 AEs	Add supportive care as indicated. Continue cabozantinib treatment at the current dose level if AE is manageable and tolerable.
Grade 2 AEs which are tolerable and are easily managed	Continue cabozantinib treatment at the current dose level with supportive care.

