Determination and attribution of DLT are critical for determining the RP2D for this study. The DLT period will include all subjects enrolled to the phase 1 component of the study who receive cabozantinib in combination with radiation therapy. The DLT period is defined as beginning on C1D8 and continuing until 28 days after completion of concurrent radiation therapy and cabozantinib. Cabozantinib is anticipated to have systemic effects at sites distant from that receiving neoadjuvant radiation treatment. It may also interact loco-regionally at the site of radiation administration. However, as the objective of this study is to assess the impact of the cabozantinib/radiotherapy combination, only those effects in the region subject to radiation therapy are considered pertinent and will be considered DLT.

DLT are defined as any Grade 3 or greater AE, occurring in the region subject to radiation therapy, at least possibly related (per investigator attribution) to concurrent radiation therapy and cabozantinib therapy. Toxicities with a clearly identified and documented alternative explanation may be deemed non-DLT. Toxicities which are clearly identified and documented as related to cabozantinib therapy only or radiation therapy only may be deemed non-DLT. Only toxicities observed in the region subject to radiation therapy will be considered DLT.

Toxicities that are Grade 3 or greater that meet the following will always be considered DLT:

1. Occur after the initiation of concurrent cabozantinib/radiation therapy until 28 days after completion of radiation therapy;
 - a. Involve the region of a subject's body that is receiving concurrent radiation therapy; and
 - b. Are of a degree or character inconsistent with anticipated radiation effects.

Dose modification guidelines are outlined in Table 5, Table 6, and Table 8 for clinically significant toxicities that are deemed to have a relation to cabozantinib. Clinically significant toxicities that are deemed to have a relationship to radiation therapy only will be managed per standard institutional practice, additional information is available in Section 10.3.

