12.2. Efficacy Analysis

Assessment of the primary efficacy analysis will take place in real time. Based on anticipated accrual of 40 evaluable subjects, if 9 or more have relapsed or died due to any cause (unless clearly documented as unrelated to investigational diagnosis, e.g., car accident) at or before one year after cabozantinib initiation, then the study will be closed to further accrual, and data will simply be collected on the remaining subjects, as specified in the protocol.

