An early stopping rule for accrual to the efficacy component of the study is to be undertaken. If 9 (nine) or more evaluable subjects are found to have died or demonstrated disease recurrence at or before 1 (one) year after cabozantinib initiation, then the efficacy component of the study will be discontinued. This assumes of a binomial probability for the primary endpoint, with a target probability of 0.90 for evaluable subjects to be alive and disease-free at one-year after initiation of cabozantinib therapy. When 9 subjects demonstrate failure with respect to the primary endpoint (disease recurrence or death from any cause), then the upper bound of the 95% confidence interval for the binomial probability distribution would no longer encompass the target probability of 0.90 ($31/40=0.775$, 95%CI:0.62-0.89). At this point, the study would be considered negative with respect to the primary endpoint, and further accrual will be discontinued.

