16. QUALITY CONTROL AND QUALITY ASSURANCE

16.1. Study Monitoring

Institutional support of trial monitoring will be in accordance with the FHCRC/University of Washington Cancer Consortium Institutional Data and Safety Monitoring Plan. Under the provisions of this plan, FHCRC Clinical Research Support (CRS) coordinates data and compliance monitoring conducted by consultants, contract research organizations, or FHCRC employees unaffiliated with the conduct of the study. Independent monitoring visits occur at specified intervals determined by the assessed risk level of the study and the findings of previous visits per the institutional DSMP.

In addition, protocols are reviewed at least annually and as needed by the Consortium Data and Safety Monitoring Committee (DSMC), FHCRC Scientific Review Committee (SRC) and the FHCRC/University of Washington Cancer Consortium Institutional Review Board (IRB). The review committees evaluate accrual, adverse events, stopping rules, and adherence to the applicable data and safety monitoring plan for studies actively enrolling or treating subjects. The IRB reviews the study progress and safety information to assess continued acceptability of the risk-benefit ratio for human subjects. Approval of committees as applicable is necessary to continue the study.

The trial will comply with the standard guidelines set forth by these regulatory committees and other institutional, state and federal guidelines.

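### Phase 2 has no prespecified toxicity threshold for pausing accrual, although the dose it inherits may have been cleared on 0 DLTs in 3 subjects

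*Combined protocol and SAP*

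**What the plan says.** **Accrual stop.** Section 12.4 states: "An early stopping rule for accrual to the efficacy component of the study is to be undertaken". It holds the one numeric accrual rule for the efficacy component: "If 9 (nine) or more evaluable subjects are found to have died or demonstrated disease recurrence at or before 1 (one) year" after starting cabozantinib, that component is discontinued. Section 12.2 has the same count: "if 9 or more have relapsed or died due to any cause". Neither section counts non-fatal toxicity.

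**Where DLTs are counted.** Section 10.2.1 states: "The DLT period will include all subjects enrolled to the phase 1 component of the study who receive cabozantinib in combination with radiation therapy". The definition is confined to Grade 3 or worse events in the irradiated region that are at least possibly related to the combination. The window runs from Cycle 1 Day 8 to 28 days after the combination is completed. No equivalent count is described for Phase 2.

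**How a dose reaches Phase 2.** Section 3.1 defines the maximum tolerated dose as the highest level with at most 1 of 6, or 0 of 3, subjects with a DLT, and gives a target rate of about 17%. After two DLTs at a higher level, the level below becomes the maximum tolerated dose; expansion of that lower level to six is not required. The recommended Phase 2 dose (RP2D) is then chosen on all safety and efficacy data, with no numeric criterion.

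**Oversight.** Section 16.1: "The review committees evaluate accrual, adverse events, stopping rules, and adherence to the applicable data and safety monitoring plan". Review is at least annual and as needed.

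**Lowest dose level.** For two or more DLTs at 40 mg or any lower level, 3.1 says that "further enrollment at that dose level will be discontinued and cabozantinib will be reduced to the next planned dose level". Table 1 ends at 20 mg. For changes within a subject, 7.1.2 adds: "Further dose reductions beyond 20 mg daily are not permitted".

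**The concern.** Most subjects are treated in Phase 2 (34 planned, against up to 12 in Phase 1), yet the measure used to choose the dose is not carried into it. Section 10.2.1 calls DLT attribution critical to setting the RP2D, and section 1.3 limits the trial to the extremities because of toxicity concerns about the combination, including fistula. Three to six subjects say little about a DLT rate. If they mislead, events will build up in Phase 2 with no agreed level at which anyone must stop and look.

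The efficacy rule cannot fill this role, because it responds to non-fatal toxicity only if that toxicity also affects relapse or death. Under the synopsis, subjects who withdraw for toxicity during the Phase 2 lead-in are not evaluable and are replaced, so they do not enter the nine-failure count, which 12.4 applies to evaluable subjects.

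**Working it through.** **1. The plan's own rule reproduces.** With 9 failures of 40, the success proportion is 31/40 = 0.775. The exact (Clopper-Pearson) 95% interval is 0.615 to 0.892, matching the stated 0.62 to 0.89. With 8 failures (32/40) the upper limit is 0.909. Nine is therefore the first count at which, in the protocol's words, "the upper bound of the 95% confidence interval for the binomial probability distribution would no longer encompass the target probability of 0.90". The efficacy rule is sound on its own terms.

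**2. It is not a toxicity rule.** If one-year relapse-free survival is 90%, the failure count is binomial(40, 0.10) and P(9 or more) = 0.015. The non-fatal toxicity rate does not enter this calculation.

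**3. What Phase 1 clearance shows.** Let p be the true DLT rate at one dose level.
- P(0 of 3) = (1−p)³
- P(level passes the 3+3) = (1−p)³ + 3p(1−p)² × (1−p)³
- Expected DLT-type events in 34 Phase 2 subjects = 34p

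| True rate p | P(0 of 3) | P(passes 3+3) | Expected in 34 |
|---|---|---|---|
| 16.7% (target, 1/6) | 0.58 | 0.78 | 5.7 |
| 33% (assumed) | 0.30 | 0.43 | 11.2 |
| 40% (assumed) | 0.22 | 0.31 | 13.6 |

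After 0 of 3, the one-sided 95% upper limit for p is 1 − 0.05^(1/3) = 0.63. The 33% and 40% rates are illustrations; the documents give no expected rate above the target.

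**4. An example boundary.** Take the smallest x with P(X ≥ x | n, 1/6) ≤ 0.05:
- n = 10: x = 5 (0.015)
- n = 20: x = 7 (0.037)
- n = 30: x = 10 (0.020)

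The exact probability of crossing at any of the three looks is 0.05 at 16.7%, 0.64 at 33% and 0.86 at 40%.

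**5. Effect of pooling Phase 1 subjects.** The figures in step 4 treat all 30 subjects as unselected. If the first three are the Phase 1 cohort that cleared the dose with 0 of 3, the first look needs 5 or more of the next 7. At 33% that has probability 21(0.33)⁵(0.67)² + 7(0.33)⁶(0.67) + (0.33)⁷ = 0.04, against 0.21 unselected. Running the same three-look calculation from 0 of 3 gives overall pause probabilities of 0.02, 0.46 and 0.73 at 16.7%, 33% and 40%.

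**6. The 20 mg sentence.** Section 3.1 applies the step-down to 40 mg and any lower level. The only lower level in Table 1 is 20 mg, and nothing is planned below it. The first half of the instruction (stop enrolling at that level) can be carried out; the second half (reduce to the next level) cannot.

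**The case against.** The strongest reply is that Phase 2 is not unsupervised. Section 12.1 requires continuous reporting of adverse events, dose interruptions and discontinuations. Section 16.1 provides committee review at least yearly and as needed, and makes applicable committee approval a condition of continuing. Section 14.5 lets the Sponsor-Investigator, the FDA, the IRB or Exelixis terminate at any time. Deaths count toward the nine failures unless clearly unrelated to the disease (12.2). The RP2D rests on all the data, so 0 of 3 permits a dose to go forward but does not force it. An institutional monitoring plan is cited that is not among the documents.

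All of this stands. A reader might infer that nothing can pause Phase 2, or that safety is judged only once everyone has been treated; the provisions just listed contradict both. The point is limited to the absence of a prespecified numeric toxicity threshold from this protocol.

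A reader might also infer that the 20 mg gap would let an unsafe dose go on accruing. It would not: 3.1 stops enrolment at that level, and a level with two or more DLTs cannot meet the definition of the maximum tolerated dose.

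Two objections to the remedy also have force. Section 9.1.3 records attribution only as related or not related to study treatment, so DLT status cannot simply be read off the existing data. The example boundary is also modest: at 33% it triggers at the first look 21% of the time and never triggers 36% of the time, and it ignores subjects enrolled while earlier DLT windows are still open.

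**Conclusion.** The point holds as a limited design gap. The protocol gives the review committees stopping rules to evaluate, but the only numeric one for Phase 2 concerns efficacy. Meanwhile a dose with twice the target DLT rate has a 30% chance of showing 0 of 3 and a 43% chance of passing the full 3+3, after which about 11 of 34 Phase 2 subjects would be expected to have a DLT-type event. These figures assume independent subjects, a constant rate and the hypothetical 33%.

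Discretionary oversight makes this an improvement that should be made, not a flaw that invalidates the trial. The 20 mg wording is a minor inconsistency: only the step after enrolment stops is undefined.

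**What to change.** 1. **Record DLTs in Phase 2.** Apply the 10.2.1 definition to Phase 2 subjects, with fields for irradiated-region location, attribution to the combination as against drug alone or radiation alone, and the window to 28 days after the combination is completed. Check that adverse-event collection covers that window: section 6.4 ends it 30 days after the last cabozantinib dose, which could come too early if the drug is stopped before radiation ends.

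2. **Add a pause-and-review rule to 12.4.** It should cover all subjects treated at the RP2D and be benchmarked to the protocol's 17%. One example is to pause accrual for DSMC review at 5 or more of 10, 7 or more of 20, or 10 or more of 30. State whether the Phase 1 subjects at that dose are counted and give the operating characteristics on that basis, since their selection lowers the chance of a pause. State also how subjects still within their window are handled.

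3. **Reconcile the 3.1 de-escalation sentence with Table 1.** Say what happens to Phase 1, and to the opening of Phase 2, after two or more DLTs at 20 mg. The clinical choice belongs to the sponsor.

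**Cost.** Protocol wording, extra DLT fields on the adverse-event form, possibly slightly longer collection for some subjects, and about a 5% chance of an unnecessary pause if the true rate is 16.7%. The sample size and the efficacy rule are unchanged.

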2. STUDY OBJECTIVES AND ENDPOINTS

2.1. Objectives

2.1.1. Primary Objectives

- Phase I: To determine if administration of cabozantinib is safe and feasible in combination with neoadjuvant radiation therapy.
- Phase II: To assess the proportion of subjects alive and free of both local and distant disease recurrence (and progression after incomplete resection) one year after treatment initiation.

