^h Baseline scans should be done within 28 days prior to enrollment, preferably as close to C1D1 as possible. Repeat imaging should be completed every 12 weeks from C1D1 (+/- 2 weeks) for one year after initiation of protocol therapy based on the date of the C1D1 visit, or until disease recurrence/progression, withdrawal of consent, death, or end of study (whichever comes first) regardless of missed or out of window doses. MRI may be used if CT is contra indicated for a subject. The same mode of imaging at screening must be used consistently throughout the study. Baseline imaging must include CAP and the affected extremity. If subjects do not have disease in the A/P, imaging moving forward after baseline may omit those areas.

ⁱ Cabozantinib will be administered daily. Subjects will complete a daily drug diary during treatment, to be reviewed on Day 1 of each cycle. Subjects with at least stable disease at the first post-RT imaging timepoint may continue to receive cabozantinib therapy for a maximum of 6 cycles, with treatment ending at least 28 days prior to any scheduled surgery, including dental surgery.

^j Prior and concomitant medications, as well as any recent procedures should be documented at baseline. Prior medications/procedures include any medications or procedures completed ≤ 28 days prior to informed consent.

^k Follow up will continue to monitor disease status by imaging assessment of, at minimum, CT Chest and the affected extremity approximately every 12 weeks (± 2 weeks), until either one (1) year has elapsed since initiating cabozantinib therapy based on the date of the C1D1 visit, death, withdrawal of consent, disease recurrence, or the study closes, whichever is the earliest. Thereafter, subjects will be followed for survival every 6 months (+/- 1 month) until 3 years have elapsed since initiating cabozantinib therapy based on the date of the C1D1 visit, disease recurrence, end-of-study, death, or withdrawal of consent, whichever is earliest. This evaluation may be made by review of publicly available information, record review and/or telephone contact.

^m Lipid panel should be fasting.

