ⁿ Optional tissue samples will be collected from archival tissue. Pre-treatment tissue should have been collected within 12 months prior to initiating protocol therapy. End of Treatment tissue samples may be collected from surgical resection, if applicable. If there is no surgical resection for any reason, end of treatment tissue samples will not be collected. No biopsies will occur solely for research collection.

^p 30 Day Follow-Up visit must occur 30 days from the date that the subject was last administered cabozantinib therapy. This visit has a window of +/- 7 days.

^q If urine protein/creatinine ratio is abnormal, a 24-hour urine collection should be collected for repeat UPC Ratio.

^r Radiation therapy may not be initiated prior to Cycle 1 Day 8. Radiation therapy must initiate within +7 days of the Cycle 1 Day 8 visit. All treatment plans for subjects that are not treated at the main study site will be submitted for review to the Sponsor-Investigator at least 1 week prior to the subject starting radiotherapy. It is recommended that outside treatment plans are received and reviewed as part of study eligibility and screening review. Review and approval of treatment plans for subjects receiving radiotherapy locally must be reviewed and approved by a radiation oncologist sub-investigator prior to initiation of radiotherapy.

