12.4. Sample Size Considerations

Phase 1: up to 12 subjects to identify the MTD, but the MTD may be reached with as few as 5 subjects.

Phase 2: For sample size determination, we assume the following:

- Null hypothesis: 1-yr relapse-free survival (local and distant) =75%
- Alternative hypothesis: 1-yr relapse-free survival (local and distant) =90%
- Alpha=0.1 (one-sided).
- Beta=0.1 (power=90%)

Total accrual=40 evaluable subjects.

Anticipate accrual of 6 evaluable subjects from phase I component of study. Therefore, 34 evaluable subjects to accrue in phase II portion of study. Subjects who withdraw for reasons other than toxicity during the DLT Period will be determined to be not evaluable and will be replaced.

Subjects are evaluated for efficacy assessment if they receive at least one dose of cabozantinib in combination with neoadjuvant radiation therapy.

Assuming a 10% drop-out/non-evaluable rate, 44 total subjects would be accrued to the efficacy component for the study to yield 40 evaluable subjects.

From the perspective of efficacy, this study is intended as a screening study of activity. Thus, avoiding a type II error (rejecting the proposed regimen as inactive, when it is an active regimen) is a major consideration. This study is not intended to provide definitive evidence of activity. Therefore, a type I error (false positive) is not considered as critical. For these reasons, we have chosen to increase the power of the study to 90% (minimizing type II errors), while relaxing constraints regarding type I. Specifically, we use a one-sided alpha of 0.10 for rejection of the null hypothesis. Use of a one-sided value is justified based on the high efficacy for *local* control of soft tissue sarcoma provided by the combination of surgery and neoadjuvant radiation therapy (~90%). It is not anticipated that distant disease control would be worsened by addition of cabozantinib to neoadjuvant radiation therapy.

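### The primary-endpoint failure event differs between sections 2.1.1, 2.2.1, 12.2 and 12.4, and no section says how to score pre-surgical progression or non-resection

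*Combined protocol and SAP*

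**What the plan says.** Four places describe the Phase II primary outcome, and they differ.

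- **Section 2.1.1 (objective):** the proportion alive and "free of both local and distant disease recurrence (and progression after incomplete resection) one year after treatment initiation".
- **Section 2.2.1 (endpoint):** the relapse rate at 12 months. Death and progression are not named.
- **Section 12.2:** accrual closes "if 9 or more have relapsed or died due to any cause" by one year, with an exception for deaths clearly documented as unrelated to the sarcoma.
- **Section 12.4 (stopping rule):** "When 9 subjects demonstrate failure with respect to the primary endpoint (disease recurrence or death from any cause", with no exception for unrelated deaths. The same paragraph sets the 0.90 target as the probability of being alive without disease one year after cabozantinib starts.

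RFS appears in the abbreviation list but is never defined. Progression-free survival is defined in the list of terms, and counts any progression, but it is not an endpoint.

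The efficacy set (list of terms and 12.4) requires only one cabozantinib dose given together with radiation. Surgery is not required. Footnote n of Table 2 foresees subjects without surgery, but only for tissue collection: "If there is no surgical resection for any reason, end of treatment tissue samples will not be collected".

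On imaging, footnote h of Table 2 runs scheduled scans for one year "or until disease recurrence/progression, withdrawal of consent, death, or end of study (whichever comes first"). Footnote k and sections 6.2.5 and 6.4.2 list recurrence, not progression, among the events that end them.

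**The concern.** Every subject enters with measurable tumour, and the endpoint clock starts at C1D1. Recurrence and relapse are natural terms once a tumour has been removed. They fit poorly while it is still there. A subject on this regimen can fail before surgery through new metastases, through growth that rules out the planned resection, or by never reaching resection. The rules in 12.2 and 12.4, which drive the count, name none of these. They also leave out progression after incomplete resection, which the objective does count.

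Section 12.2 applies the rule in real time, in an open-label single-arm trial. Without a written rule, each such case would be decided after its outcome is known. Two things depend on that decision: the test of 75% against 90%, and the nine-failure accrual stop.

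**Working it through.** **1. The plan's own figures reproduce.** Inputs from 12.4: "Null hypothesis: 1-yr relapse-free survival (local and distant) =75"%, "Alternative hypothesis: 1-yr relapse-free survival (local and distant) =90"%, "Alpha=0.1 (one-sided"), power 90%, 40 evaluable.

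n = [(z₀.₉₀·√(p₀q₀) + z₀.₉₀·√(p₁q₁)) / (p₁ − p₀)]²
= [(1.2816 × 0.4330 + 1.2816 × 0.3000) / 0.15]² = 39.2, so 40.

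The exact (Clopper-Pearson) 95% interval for 31/40 is 0.615 to 0.892, matching the stated 0.62 to 0.89. For 32/40 the upper limit is 0.909, so nine is the first failure count that excludes 0.90.

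**2. Which cases does each text name?** All cases are alive at one year.

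| Case | 2.1.1 | 2.2.1 | 12.2 | 12.4 event list | 12.4 target state |
|---|---|---|---|---|---|
| New metastasis before surgery | arguable | arguable | arguable | arguable | not a success |
| Local progression before surgery | not named | not named | not named | not named | not a success |
| Never resected, tumour present | not named | not named | not named | not named | not a success |
| Progression after incomplete resection | failure | not named | not named | not named | not a success |

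Arguable means that the case counts only if distant recurrence or relapse is read to include a first metastasis with the primary tumour still in place.

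**3. How long is the exposed period?** Section 6.2.1 gives one week of lead-in, an RT start window of up to one further week, typically 5 to 6 weeks of RT, and typically 4 to 6 weeks to surgery. The shortest typical path is 1 + 5 + 4 = 10 weeks and the longest is 1 + 1 + 6 + 6 = 14 weeks, or 19% to 27% of 52 weeks. If six 21-day cycles (read as the total) and the 28-day gap are used, surgery falls at 18 + 4 = 22 weeks, or 42%. The first scheduled scan, at week 12 ± 2, falls around typical surgery.

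**4. Size, as an illustration.** Two inputs are assumptions. The first is k, the expected number of the 40 who fail in an unnamed way, are alive at one year and are not scored as failures. The second is the success cut. The plan states none; 34/40 is the smallest cut with exact size at or below 0.10 (size 0.096, power 0.900). The true RFS, with these subjects counted as failures, is set at 75%. The scored rate is then 0.75 + k/40, and the tails are binomial with n = 40.

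| k | Scored RFS | P(≥34/40) | P(≥32/40) | P(9 or more counted failures) |
|---|---|---|---|---|
| 0 | 0.750 | 0.096 | 0.300 | 0.700 |
| 1 | 0.775 | 0.173 | 0.439 | 0.561 |
| 2 | 0.800 | 0.286 | 0.593 | 0.407 |
| 3 | 0.825 | 0.435 | 0.743 | 0.257 |
| 4 | 0.850 | 0.607 | 0.865 | 0.135 |

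The 32/40 column shows the result if merely avoiding nine failures were taken as success. The last column assumes that all 40 are followed for one year.

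**The case against.** The strongest reply is that the plan never says these subjects are successes. Section 12.4 sets the target as being alive without disease, and a subject with the tumour in place or with metastases does not meet it. Distant recurrence in 2.1.1 can also be stretched to cover a metastasis found before surgery. This stands. A reader might infer that the plan counts such subjects as successes, but the documents are inconsistent and partly silent, and they do not say so. The conflict between the target state and the event list still has to be resolved.

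Two further inferences go too far. One is that the event list begins only after surgery. Deaths before surgery do count under both 12.2 (unrelated deaths excepted) and 12.4, so the dispute concerns living subjects only. The other is that someone who progresses before surgery would not be scanned again. Footnote h alone points that way. Footnote k and sections 6.2.5 and 6.4.2 continue 12-weekly imaging to one year unless recurrence or another listed event ends it, and 6.2.5 allows unscheduled scans on suspicion of recurrence or progression.

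It can also be said that 12.4 calls this a screening study in which a type I error matters less. That explains the choice of 0.10. It does not cover an unquantified increase above 0.10.

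**Conclusion.** The primary-endpoint failure event is inconsistent across four sections, and the rules that drive the count omit cases the design makes possible. One of these, progression after incomplete resection, is counted by the objective itself. The affected subjects remain in the denominator. This is more than missing detail, because it bears on both the primary result and the accrual stop.

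What holds without assumption is the direction of the miscount. Each such subject not scored as a failure adds 1/40, or 2.5 percentage points, to the observed 1-year RFS and removes one event from the nine-failure count. The probabilities are illustrative, since they rest on an assumed number of uncounted failures and on a 34/40 cut that the plan does not state.

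A reader might also infer that the bias against the 75% benchmark must favour the regimen. The documents do not support that, because they do not say how the 75% was derived or which events it counts. The false-positive figures hold only if the 75% treats these cases as failures. If it leaves them out, counting them in the trial alone would work against the regimen.

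**What to change.** Define the event once, consistent with being alive and without disease one year from C1D1, and use it in 2.1.1, 2.2.1, 12.2 and 12.4 and in the synopsis. Failure would be the first of:

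- new regional or distant disease at any time, including before surgery;
- progression that precludes the planned resection;
- local recurrence after resection;
- progression after incomplete resection;
- death, under one rule that reconciles 12.2 with 12.4.

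Pre-specify how subjects not resected for reasons other than progression are scored, with a sensitivity analysis under the opposite scoring. Refusal of surgery and unrelated medical reasons fall here, and the primary scoring is the sponsor's choice. Confirm that the 75% null counts the same events. Reconcile footnote h with footnote k, 6.2.5 and 6.4.2 on whether progression ends scheduled imaging.

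The cost is wording in these places. The observed 1-year RFS may be slightly lower. The sample size stays at 40, provided 75% and 90% still apply to the event as defined.
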